13.5.5 The Pharmacokinetics of Anetumab ravidansine

The analysis of the pharmacokinetics of anetumab ravidansine (including anti-drug conjugate (ADC) anetumab ravidansine, total antibody, DM4 (BAY 1006640) and DM4-Me (BAY 1006641)) will be largely descriptive. Changes over time will be plotted and assessed for each patient.

13.5.6 Megakaryocyte Potentiating Factor (MPF)

The test for MPF is quantitative and continuously distributed. A reference value will be provided and samples with tumor antigen MPF levels above the reference value will be considered positive. The relative changes in biomarker levels will be compared by best overall response groups using the non-parametric Wilcoxon rank-sum test. Also, the associations between changes in MPF levels and ordered response categories (i.e. CR-PR-SD-PD) will be assessed with the Jonckheere-Terpstra test for trend.

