1.2 Secondary Objectives

1.2.1 To determine the progression free survival of anetumab ravidansine and pembrolizumab compared to pembrolizumab alone.

1.2.2 To evaluate the pharmacodynamic effects of anetumab ravidansine and pembrolizumab on soluble megakaryocyte potentiating factor (MPF).

1.2.3 To evaluate the pharmacokinetics of anetumab ravidansine and pembrolizumab.

1.2.4 To evaluate mononuclear phagocyte system (MPS) function, Fc γ Rs, hormone and chemokine mediators as methods to evaluate factors affecting the pharmacokinetics and pharmacodynamics of these agents.

1.2.5 To determine the incidence of antibodies directed against anetumab ravidansine.

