9.3.3 Megakaryocyte Potentiating Factor (MPF)

MPF is cleaved from the amino terminus of a precursor protein that leaves mesothelin linked to the cell surface by glycophosphatidylinositol (65, 66). Thus, serum MPF is correlated with mesothelin expression and provides a blood-based marker of mesothelin-positive tumor burden. In a recently published clinical trial that tested the anti-mesothelin immunotoxin SS1P in patients with MPM (67), serum MPF levels correlated with radiographic responses. Accordingly, it is hypothesized that serum MPF may correlate with radiographic responses to treatment with anetumab ravtansine in this clinical trial.

In the current trial, MPF is not intended to provide clinical guidance. Results will be provided at an interim point and at the end of the study when all of the samples have been collected to explore the associations of MPF with treatment response.

Testing for MPF has demonstrated a sensitivity of < 10 pg/mL with an analytic range of 0.02-100 ng/mL. With adjustments for 5-fold sample dilution, the test has a quantification range of 0.10-500 ng/mL. The current upper reference value is 1.2 mg/mL, with values above the reference level considered to be elevated.

The test of MPF test was effective in mesothelioma patients with elevated MPF. In mesothelioma patients, MPF was elevated in a high percentage of these patients (70%). Thus, statistically significant data can be obtained with as few as 20 treatment naïve mesothelioma patients in our study.

Blood will be collected from patients concurrently with clinical blood draws, when possible, in order to minimize any discomfort.

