- g: For Phase 2, submission of a tissue sample at pre-registration is required to perform the mesothelin expression assay to establish eligibility. Archived tumor tissue may be submitted; if archived tumor tissue is not available to establish eligibility, a fresh tumor tissue sample must be obtained by biopsy. If a biopsy is required, it may be performed ≤ 28 days prior to start of therapy. For Phase 1 subjects, submission of archived tumor tissue, if available, is required for mesothelin expression testing. Please refer to Section 9.
- h: For subjects in both Phases 1 and 2, submission of a stored tissue sample is mandatory, *if available*, for the tissue expression of PD-L1: do **not** perform a biopsy solely to provide tissue for this correlative. Tumor tissue may be submitted as blocks or slides; please refer to section 9.

i: Blood samples for correlates are collected as follows (see also Section 9):

- 1) Phase 1 and Phase 2 Group 2 patients only: Pharmacokinetics of anetumab raptansine (including anetumab raptansine ADC, anetumab raptansine total antibody, and DM4/DM4-Me) on C1D1: pre-treatment, end of anetumab raptansine infusion (+/- 15 minutes), and 7 hours after the end of anetumab raptansine infusion (+/- 15 minutes); C1D8: any time. Note: These may be discontinued for patients who discontinue anetumab raptansine.
- 2) Phase 1 and Phase 2 Group 2 patients only: Anti-anetumab raptansine antibodies (including anetumab raptansine ADA and neutralizing antibodies) pre-dose on Day 1 of Cycles 1, 3, 6 and 9 and pre-dose every 3 months after cycle 9 in the first year and every 6 months in the second year of treatment. Note: These may be discontinued for patients who discontinue anetumab raptansine.
- 3) Megakaryocyte Potentiating Factor: pre-study, C2D1, and C4D1.
- 4) Mononuclear Phagocyte System-Fc γ R: C1D1, C1D8, C3D1 and C3D8.
- 5) Chemokine Mediators of Mononuclear Phagocyte System: C1D1, C1D8, C3D1 and C3D8.
- 6) Bim in Tumor Reactive T cells and soluble PD-L1: pre-study, C2D1, and C4D1.

j: For sites and patients that agree to participate, PRO-CTCAE is completed by ePRO application on patients' personal devices or on a tablet kept at the study site weekly during the first 3 cycles and at off-study. Questionnaires should be administered prior to treatment on days study treatment is administered. See Appendices C and D.

k: Off-study evaluation to be performed at 30 ± 3 days after the last dose of study drug.

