13.5.3 Progression Free Survival

Progression free survival is defined as the start of treatment to the earliest date that

disease progression is objectively documented or death due to any cause. The distribution of progression-free survival will be estimated using the method of Kaplan-Meier. The comparison of progression-free survival between two treatment arms will be based on the log-rank test.

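### No stated analysis answers secondary objective 1.2.2 on MPF, and the planned response-association tests do not say how treatment arm is handled

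*Combined protocol and SAP*

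**What the plan says.** Section 1.2, objective 1.2.2, reads: "To evaluate the pharmacodynamic effects of anetumab ravidansine and pembrolizumab on soluble megakaryocyte potentiating factor (MPF". It names no comparator, whereas objective 1.2.1 on progression-free survival names pembrolizumab alone.

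Section 13.5.6 holds the whole MPF analysis. First: "The relative changes in biomarker levels will be compared by best overall response groups", by a Wilcoxon rank-sum test. Second, a Jonckheere-Terpstra test of "the associations between changes in MPF levels and ordered response categories" from CR to PD. It does not say how response is split for the two-group test, which visit supplies the change, which arms are included, or whether arm is accounted for.

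Section 9.3.3 gives the purpose of the assay in the same terms: to "explore the associations of MPF with treatment response".

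The study calendar (section 10, note i) lists "Megakaryocyte Potentiating Factor: pre-study, C2D1, and C4D1" with no restriction by group. The pharmacokinetic item in the same note is restricted: "Phase 1 and Phase 2 Group 2 patients only: Pharmacokinetics of anetumab raptansine". The anti-drug antibody item carries the same restriction.

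Other entries in section 13.5 do name the contrast between arms. For example, in 13.5.3: "comparison of progression-free survival between two treatment arms will be based on the log-rank test". Duration of response, overall survival and adverse events are handled likewise.

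**The concern.** The objective and the analysis ask different questions. The objective concerns the effect of treatment on the marker. The analysis asks whether change in the marker goes along with response, whatever the treatment. A plan followed to the letter would produce two p-values about response and none about a drug effect, and those p-values might then be reported under objective 1.2.2.

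The second issue is arm. The combination arm contains the drug aimed at mesothelin, and MPF comes from the mesothelin precursor (section 2.4.1). The trial is also powered for a higher response rate in that arm. If both arms enter one unstratified test, responders come disproportionately from the combination arm. A drug effect on MPF that has nothing to do with response could then be read as MPF tracking response.

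**Working it through.** **Objective against analysis**

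| Question | Where an answer could come from | Planned? |
|---|---|---|
| Does MPF change differ between arms? | Between-arm comparison | No |
| Does MPF change from baseline on treatment? | Within-arm change at C2D1, C4D1 | No |
| Does MPF change go with response? | Wilcoxon and trend tests, 13.5.6 | Yes |

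Only the third row is planned. The first two are the ones that bear on 1.2.2. The samples for both will exist, because MPF is drawn in both groups.

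**Reproducing the design figure**

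Section 13.5.6 attaches no significance level, power or effect size to MPF. Section 9.3.3 remarks that as few as 20 treatment-naive patients could suffice, but names no test or effect, so there is nothing to reproduce. The figure that can be checked is the primary design in 13.1.3.3: 49 per arm, 20% vs 40%, one-sided 0.10, 80% power.

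- SE under the null = √(2 × 0.3 × 0.7 / 49) = 0.0926
- SE under the alternative = √((0.2 × 0.8 + 0.4 × 0.6) / 49) = 0.0904
- Power = Φ((0.20 − 1.282 × 0.0926) / 0.0904) = Φ(0.90) = 0.816

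This agrees with the stated 80%. Simulation with the futility look included also gives 0.816.

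**What happens if the arms are combined without stratification**

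Inputs from the documents: 49 per arm and the response rates of 20% and 40% (13.1.3.3). Assumptions not in the documents: those rates hold; response is split into responders and non-responders; MPF change is normal with unit SD within arm; it is unrelated to response within arm; the combination arm is shifted by d SD; the test is two-sided at 5%; no samples are missing; phase 1 patients are left out.

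1. Expected responders: 49 × 0.2 + 49 × 0.4 = 9.8 + 19.6 = 29.4. Expected non-responders: 39.2 + 29.4 = 68.6.
2. Combination share: 19.6 / 29.4 = 0.667 of responders, 29.4 / 68.6 = 0.429 of non-responders.
3. Spurious responder vs non-responder difference: d × (0.667 − 0.429) = 0.238 d SD.
4. Rough check by normal approximation for a difference in means. The variance within a response group is 1 + d² × share × (1 − share). At d = 1 these are 1.222 and 1.245, so SE = √(1.222/29.4 + 1.245/68.6) = 0.244 and the standardised difference is 0.238/0.244 = 0.97. The rejection probability is Φ(0.97 − 1.96) + Φ(−0.97 − 1.96), about 16%. The same steps give standardised differences of 0.27 at d = 0.25 and 0.53 at d = 0.5, hence about 6% and 8%.
5. Simulation of the rank tests themselves, 8,000 replicates per setting:

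| Shift d (SD) | Unstratified Wilcoxon by response, 20% vs 40% | Stratified by arm (van Elteren), 20% vs 40% | Unstratified, 20% vs 20% | Direct between-arm Wilcoxon (power), 20% vs 40% |
|---|---|---|---|---|
| 0 | 5.5% | 5.3% | 5.0% | 5.5% |
| 0.25 | 5.7% | 4.9% | 5.0% | 22% |
| 0.5 | 7.6% | 5.0% | 4.8% | 68% |
| 0.75 | 11.4% | 4.8% | 4.8% | 95% |
| 1.0 | 15.9% | 5.3% | 5.1% | 99.7% |

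The first three result columns are false-positive rates for a link with response. The last is power for the drug effect, which is the question nearest to 1.2.2; its entry at d = 0 is the test's size.

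**The case against.** Four points can fairly be made for the plan.

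- **The objective names no comparator.** A reader might infer that 1.2.2 demands a between-arm test. The text does not say so, and a within-arm change from baseline could serve it. This stands, but no within-arm analysis is planned either, so the gap remains.
- **The plan never says that the arms are pooled.** A reader might infer this from the absence of an arm factor and from sampling in both groups. Section 9.3.3 states its hypothesis for treatment with anetumab ravtansine, which would fit an analysis of combination-treated patients only, where arm cannot confound. This stands: the supportable statement is that the handling of arm is unspecified. Likewise, the split into responders and non-responders is a natural reading and not the plan's wording.
- **Confounding is conditional.** Sections 2.4.1 and 9.3.3 present MPF as a marker of mesothelin-positive tumour burden that followed radiographic response. If anetumab ravtansine lowers MPF only through shrinkage that the response category captures, MPF is independent of arm given response and a combined test is not confounded. The calculation assumes the opposite extreme: a shift with no link to response. This stands, and it makes the figures an illustration, not a forecast.
- **Little hangs on the result.** Section 9.3.3 says that MPF will not guide care and describes the association work as exploratory. No decision rule depends on it. This stands and limits the severity. MPF is nevertheless a listed secondary objective.

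**Conclusion.** The concern holds in two parts of unequal strength.

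The first is firm and needs no assumption. Objective 1.2.2 concerns the drugs' effect on MPF, and no stated analysis estimates or tests such an effect, between arms or within an arm.

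The second is conditional. Section 13.5.6 leaves the handling of arm open. If the arms are combined unstratified, the false-positive rate of the response association rises from 5% to about 5-6%, 8% and 16% at arm shifts of 0.25, 0.5 and 1.0 SD. That requires the powering rates of 20% and 40% to hold and an arm effect on MPF that response does not explain. It also rests on normal changes, a two-sided 5% level and complete samples. With equal response rates the test stays at about 5% at any shift.

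The stronger statement that the MPF analysis is confounded by arm is not supported: the documents neither specify pooling nor establish an effect on MPF apart from response. The primary endpoint is untouched. Severity: minor.

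**What to change.** Amend section 13.5.6 in two places.

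1. For objective 1.2.2, add a comparison of MPF change from baseline at C2D1 and C4D1 between the randomised arms, for example on log MPF adjusted for baseline log MPF, and report within-arm change. Phase 1 patients were not randomised and belong only in the within-arm description.
2. For the response association, state which patients are included and how best overall response is split. Stratify the Wilcoxon test by arm (van Elteren). Stratify the trend test by arm too, or show it by arm where categories are sparse.

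The cost is SAP wording and slightly more analysis; no sample, visit or patient is added. The main drawback is sparse response categories in the control arm, where 49 × 0.2 gives about 10 responders. With complete samples, the between-arm comparison would have about 68% power at a shift of 0.5 SD and 95% at 0.75 SD, so at 0.5 SD or below it is better reported as an estimate with its interval than as a test alone.

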13.5.7 MPS-Fc_γRs and chemokine mediators of MPS

The mean equivalent soluble fluorophore (MESF) and antibody bound to cell (ABC) will be determined for each specimen. Linear regression will be used to explore the linear relationship between the continuous values of these MPS-Fc_γRs probes and anetumab ravidansine levels.

The concentrations of CCL2 and CCL5 will be determined for each specimen. Linear regression will be used to explore the linear relationship between the continuous values of these chemokines and anetumab ravidansine levels.

13.6 Analysis of Exploratory Endpoints

13.6.1 Measurements of Bim in T_{TR} as a predictor of responses to treatment.

Based on previous experiences with the distribution of Bim in T_{TR}, it is anticipated that a non-parametric test such as the Mann-Whitney test should be used to compare Bim in T_{TR} between subjects that do and do not respond to therapy.

13.6.2 Measurements of soluble PD-L1 as a predictor of responses to treatment.

Based on previous experiences with the distribution of sPD-L1, it is anticipated that a non-parametric test such as the Mann-Whitney test should be used to compare sPD-L1 between subjects that do and do not respond to therapy.

13.6.3 PD-L1 expression in archival tissue as a predictive marker of response to pembrolizumab-based therapy.

We will compare whether there is a difference in the number of responders with 50% or greater PD-L1 tumor cell expression and those without with the Chi-square test (or Fisher's exact test if the data in the contingency table is sparse).

13.6.4 PRO-CTCAE

Protocol investigators should provide appropriate analysis of the data and account for missing data.

13.7 Data and Safety Monitoring

13.7.1 DSMB Review

The principal investigator and the study statistician will review the study at least every quarter to identify accrual, adverse event, and any endpoint problems that might be developing. The accrual and safety data provided by Theradex for this trial will be reviewed and monitored by the Mayo Clinic Cancer Center (MCCC) Data Safety Monitoring Board (DSMB) at least twice a year, or more frequently as warranted.

13.7.2 PRO-CTCAE

PRO-CTCAE data should not be used in adverse event stopping rules.

13.7.3 Phase 2 Adverse Event Stopping Rule

The stopping rule applies to each group independently.

The stopping rule specified below is based on the knowledge available at study development. We note that the rule may be adjusted in the event of either (1) the study re-opening to accrual or (2) at any time during the conduct of the trial and in consideration of newly acquired information regarding the adverse event profile of the treatments under investigation. The study team may choose to suspend accrual because of unexpected adverse event profiles that have not crossed the specified rule below.

Accrual will be temporarily suspended to both groups if at any time we observe events considered at least possibly related to study treatment (i.e., an adverse event with attribute specified as “possible,” “probable,” or “definite”) that satisfy either of the following:

- if 4 or more patients in the first 20 treated patients in either group experience a grade 4 or higher non-hematologic adverse event at least possibly related to treatment.
- if after the first 20 patients have been treated, 25% of all patients in either group experience a grade 4 or higher non-hematologic adverse event at least possibly related to treatment.

We note that we will review grade 4 and 5 adverse events deemed “unrelated” or “unlikely to be related”, to verify their attribution and to monitor the emergence of a previously unrecognized treatment-related adverse event.

After consideration by the Principal Investigator and the statisticians and consultation with CTEP and CIRB, a decision will be made as to whether and how the study will proceed.

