5.2 Phase 1 Study

Since this combination has not been studied to date, the first 6 patients treated at dose level 1 will be used as an early safety lead-in per Section 13.2. If 2 or more patients experience a dose-limiting toxicity (DLT) as defined below, then the starting dose level will be adjusted and additional cohorts may be evaluated at dose levels -1 and -2 in the safety lead-in stage as described in section 13.1.2. The acceptable DLT rate is 0.20.

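### The phase 2 adverse-event stopping rule steps from 4 events at 20 patients to 6 at 21, with no rationale, target rate or operating characteristics

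*Combined protocol and SAP*

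**What the plan says.** The rule is in section 13.7.3. Its first limb is met "if 4 or more patients in the first 20 treated patients in either group experience" the monitored event. Its second limb is met "if after the first 20 patients have been treated, 25% of all patients in either group experience" that event. In both limbs the event is "a grade 4 or higher non-hematologic adverse event at least possibly related to treatment".

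Monitoring is by arm ("The stopping rule applies to each group independently"). The limbs are alternatives, checked at any time: a crossing is a set of events "that satisfy either of the following". The consequence is shared: "Accrual will be temporarily suspended to both groups", after which the investigator and statisticians consult and decide how to proceed.

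The section also lets the team suspend accrual for unexpected toxicity below the boundary, allows the rule to be adjusted, and requires review of grade 4 and 5 events judged unrelated or unlikely to be related. Section 13.7.1 adds review by the principal investigator and statistician at least quarterly, and by the DSMB at least twice a year.

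Section 13.7.3 states no acceptable or unacceptable event rate and no suspension probabilities. By contrast, sections 13.1.3.1 and 13.1.3.3 tabulate operating characteristics for the phase 1 rule and the efficacy design.

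**The concern.** Both limbs count the same event in the same group, so they should form one coherent boundary. Instead, one further patient raises the count needed for suspension by two. An arm with 4 events in 20 is paused. An arm with 3 in 20 and 2 in the next 2 patients (5/22, 22.7%) is not, although its observed rate is higher and rests on more patients.

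No other numeric safety boundary applies in phase 2. With a planned 49 evaluable patients per arm, 49 − 20 = 29 patients per arm fall under the second limb. At the maximum accrual of 110 (about 55 per arm) the figure is 55 − 20 = 35. What is at stake is the rule's ability to pick up a moderately raised rate of severe related toxicity in those patients.

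**Working it through.** **Inputs.** From section 13.7.3: threshold 4 for n ≤ 20, and the smallest whole number at or above 0.25n for n > 20. From sections 13.1.3.3 and 13.3.1: 49 evaluable patients per arm, and at most 110 in total. True event rates are assumptions, because the documents give none; 5% to 40% is shown. The plan states no operating characteristic for this rule, so there is no figure to reproduce first.

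**Boundary counts.**

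| n in group | count needed | proportion |
|---|---|---|
| 10 | 4 | 40.0% |
| 16 | 4 | 25.0% |
| 20 | 4 | 20.0% |
| 21 | 6 (0.25 × 21 = 5.25) | 28.6% |
| 24 | 6 | 25.0% |
| 25 | 7 | 28.0% |
| 49 | 13 (0.25 × 49 = 12.25) | 26.5% |
| 55 | 14 (0.25 × 55 = 13.75) | 25.5% |

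The required proportion falls until n=20, steps up once, then moves in a saw-tooth at or just above 25%. With at most 3 events in the first 20, a group can stand at 5/22 (22.7%), 8/33 (24.2%) or 12/49 (24.5%) without meeting either limb.

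**Single-look probabilities**, P(X ≥ c) with X binomial(n, p):

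| true rate p | n=20, c=4 | n=21, c=6 | n=49, c=13 |
|---|---|---|---|
| 15% | 0.352 | 0.083 | 0.026 |
| 20% | 0.589 | 0.231 | 0.166 |
| 25% | 0.775 | 0.433 | 0.456 |
| 30% | 0.893 | 0.637 | 0.750 |
| 40% | 0.984 | 0.904 | 0.983 |

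**Sequential probabilities per group.** These come from an exact patient-by-patient binomial recursion that checks the boundary after each patient and assumes each outcome is known before the next patient enters. The comparator keeps the 20% fraction after patient 20 (5 events at n=21–25, 10 at n=49). It is an illustration only, not a proposed rule. The conditional probability is (P49 − P20)/(1 − P20), from unrounded values.

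| true rate | by n=20 | by n=49, as written | by n=49, 20% carried forward | 21–49 given none by 20, as written | same, 20% carried forward |
|---|---|---|---|---|---|
| 5% | 1.6% | 1.6% | 1.8% | 0.0% | 0.2% |
| 10% | 13.3% | 13.6% | 17.1% | 0.3% | 4.4% |
| 15% | 35.2% | 37.1% | 47.4% | 2.9% | 18.9% |
| 20% | 58.9% | 63.6% | 76.4% | 11.7% | 42.5% |
| 25% | 77.5% | 83.9% | 92.5% | 28.7% | 66.8% |
| 30% | 89.3% | 94.7% | 98.3% | 50.9% | 84.4% |
| 40% | 98.4% | 99.8% | 100.0% | 86.6% | 98.1% |

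**Trial level.** Either group suspends both. If both groups share the same true rate and are independent, P(trial) = 1 − (1 − P49)². At 10%: 1 − (1 − 0.136)² = 25.3% as written, against 1 − (1 − 0.171)² = 31.3%. At 15%: 60.4% against 72.4% (unrounded inputs).

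**The case against.** The limbs do not contradict each other and can be run as written. Three further points on the plan's side stand.

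- **Size depends on the base.** The conditional contrast is large, but at a 30% rate only 1 − 0.893 = 10.7% of groups pass patient 20. The unconditional gain from carrying 20% forward is 12.7, 8.6 and 3.6 points at 20, 25 and 30%, and 0.2 points at 40%.
- **Tightening has a price.** At a true 10% rate, later suspension of a group that has passed patient 20 goes from 0.3% to 4.4%, and the shared suspension adds to this at trial level. Since no acceptable rate is stated, extra pauses at 10% or 15% might count as false alarms.
- **There are backstops.** Discretionary suspension, quarterly review and DSMB review can all act below the boundary. They set no number, however, and do not explain the step.

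A reader might go further than the documents allow in three ways:

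- *That the rule is weakest once most patients are exposed.* It is not. The required proportion is highest before n=16, and the cumulative chance of suspension never falls with exposure.
- *That 5 of 23 never suspends.* It escapes only if at most 3 of the 5 events are among the first 20. Otherwise the first limb has already been met.
- *That the phase 1 acceptable DLT rate of 0.20 shows 25% to be too lenient.* Section 5.2.1 defines a different event: it covers two cycles, includes related hematologic grade 4 events and also counts some non-resolving lower-grade events. It is no benchmark for the phase 2 event.

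**Conclusion.** The point holds as an unexplained misfit between two limbs of one rule. The boundary steps from 20% to at least 25% after patient 20, and this weakens detection of moderately raised true rates, about 15–30%, in groups that pass patient 20. At a true 20% rate such a group has an 11.7% chance of suspension by patient 49, against 42.5% in the illustration. Over all groups the figures are 63.6% and 76.4%. At 40% or more the overall difference is negligible.

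These sizes rest on assumed true rates, immediate knowledge of outcomes and 49 treated patients per group. The trial-level figures also assume equal rates in independent groups. The documents do not show which threshold is right, and this review does not say.

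**What to change.** Reconcile the two limbs. The study team should state one unacceptable rate for the monitored event and derive both limbs from it, so that the required proportion does not step up after patient 20 apart from whole-number rounding. If the step is intended, the section should say why.

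In either case, print the boundary count for each n from 20 to 55, with per-group and trial-level suspension probabilities at true rates of 5% to 30%.

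The cost is one rewritten bullet and a small table. If the team chooses a tighter later boundary, there is also a higher chance of a pause, of the order shown above at 10% and 15%. A crossing only halts accrual temporarily for review, and section 13.7.3 already allows the rule to be adjusted.
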